10.0 Study Calendar

Table 4. Outcome Measures by Aims and Assessment Time Points

	Measures	Before Surgery (T1)	Pre-Discharge (T2)	Day 7 (T3)	Day 14 (T4)	Day 30 (T5)	Day 60 (T6)	Day 90 (T7)
Preop Functional Assessment	6 Minute Walking Time (6MWT)	X						
	Timed Up and Go (TUG)	X						
	Short Physical Performance Battery (SPPB)	X						
Aim 1	Functional Recovery (steps taken, sedentary time)	X	X	X	X	X	X	X
	General Symptoms - MD Anderson Symptom Inventory (MDASI)	X	X	X	X	X	X	X
Aim 2	Post-Operative Complications – CCI		X	X	X	X	X	X
	Hospital Readmissions			X	X	X	X	X
Aim 3	Early withdrawal (dropout, loss of device)							Throughout the Study
Aim 4	Open-Ended Patient Exit Survey							X
	Patients/Families/Surgeon/Nurses Experience – Focus Groups							Year 2-3, Month 22-30

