MD Anderson Symptom Inventory (MDASI) - The MDASI is a validated measure of 13 common cancer-related symptoms: pain, fatigue, nausea, sleep, distress/anxiety, shortness of breath, memory, appetite, dry mouth, drowsiness, sadness, vomiting, and numbness/tingling. Each symptom's severity is rated on a 10-point scale. A score of 1-3 indicates mild intensity, and 4-10 moderate to severe intensity. Patients also rate how much their symptoms interfered with 6 common functional domains: walking, activity, working/housework, social relationships, enjoyment of life, and mood. A movement of 1.2 points is clinically meaningful. The MDASI has been validated in surgical populations; Cronbach Alpha reliability ranges from 0.82 to 0.94.^{46, 83}

Functional Activity (Actigraph) – Based on published recommendations on best practice in use of accelerometry⁸⁴⁻⁸⁷, we will initiate several parameters to ensure that the data captured is reliable. First, data will be collected in 1 second epochs and reintegrated to 60 second epochs for analysis. Non-wear time will be defined as 60 minutes of continuous 0 counts. A minimum of 4 weekdays and 1 weekend day with at least 600 minutes (10 hours) of daily wear time will be considered valid. In order to be considered a valid day, patients need to wear the accelerometer for at least 10 waking hours (600 minutes). Data capture will focus on the following: 1) number of steps taken per day and 2) sedentary time. Recommended activity counts per minute (cpm) cutpoints will be used to categorize sedentary time (<100 cpm) from light-intensity physical activity (100–1951 cpm) and moderate/vigorous intensity physical activity (≥ 1952 cpm).

Comprehensive Complications Index (CCI) - The CCI[®] summarizes the entire patient postoperative experience with respect to complications (on a scale from 0 to 100), and is based on the established Clavien-Dindo classification. The CCI[®] was validated in a study with 1299 participants, and external validity was tested in a randomized trial evaluating pancreas, esophageal, and colon resections.^{88, 89}

Readmissions - Electronic health record audits will capture: 1) 30, 60, and 90 day inpatient readmissions, 2) reasons for readmissions, and 3) ER visits. If the patient seeks emergent care outside of the primary institution, the patient's permission will be obtained to review these records.

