13.2 Statistical Analysis Plan

Data Management - We expect a total of 12 symptom evaluations per participant over the 3-4 month study duration. With a total sample of 332, this yields approximately 4,000 data collection encounters overall. We expect a large number of daily steps data observations per subject, as functional recovery data will be continuously recorded on a daily basis over the study duration.

Data will be transferred in real-time (within 2 minutes of participant completion) from TapCloud™ to a REDCap (Research Electronic Data Capture) study database. Daily step count will be continuously transferred to the study database in real-time. The database resides in secure COH research networks for research team access only. An assigned master's-level Statistical Research Associate (SRA) with paid effort on the project will be responsible for coordinating monthly data transfer, auditing, and data cleaning. In the process of data transfer and mergers, the study biostatistician ([name]), SRA, and TapCloud™ representative will audit and clean the data, apply formats in statistical software, and export data into REDCap database.

Handling Missing Data and Lost to Follow-Up - We will integrate the following strategies to prevent, detect, and remedy missing data in real time. First, participants will receive a total remuneration of \$50 for providing data. Second, research staff will provide telephone/email reminders before each of the scheduled data collection timepoints to maximize adherence. Regular contact will also be provided to remind participants to wear the accelerometer. Third, research staff will provide each participant with a simple study calendar with data collection dates. Fourth, if no data is completed by participants, research staff will contact the participant in real-time to engage and assess. The Statistical Methods section below describes how data missing not at random will be handled in the analyses.

Preliminary Analysis - Descriptive statistics will be used to summarize all variables. Characteristics of participants at baseline will be reported in tabular form using appropriate descriptive statistics. Prior to hypothesis testing, the relationship between demographic variables and primary outcome variables (daily step count, postop complications) will be examined. Significant relationships/correlations will guide the addition of demographic variables to the analysis.

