Heterogeneity of Treatment Effect - Exploratory use of interaction terms will assess whether significant effects of the study intervention differ by sex or by age (i.e., above vs below 70 years). If found to be present, any such heterogeneity of treatment effect, not having been hypothesized in advance, will be reported as a preliminary finding that awaits confirmation in future studies.

Internal/External Validity and Avoidance of Bias - To limit possible confounding of the primary results, analyses of the prespecified hypotheses will be adjusted for covariates (age, sex, physical fitness at pre-surgical baseline). To assess the representativeness of study participants, their demographic characteristics (sex, age) will be compared to those of eligible patients who are approached for consent but decline to participate in the study. Our digital engagement platform will initiate reminder systems to reduce loss to follow-up.

Statistical Methods by Study Aims - Characteristics considered as potential covariates in all analyses will be age, sex, surgical technique, residential setting, and physical fitness at preoperative baseline. Any covariate that improves the model's fit to the observed data will be retained in the final analysis.

The analyses for Aims 1-3 will be by intention to treat (ITT); the ITT population will include all subjects who have given informed consent, been randomized to intervention or control arm, and undergone the planned cancer surgery.

Aim 1 – Allowing for an anticipated 20% attrition in use of accelerometer by Day 14 across both trial arms, an initial sample size of 332 (randomized 1:1) will provide (per East 6.5 software)

80% power to detect the hypothesized 14% difference in slope due to study intervention, using a 1-sided, repeated measures-difference of slope test with alpha=0.025.

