The Aim's primary endpoint will be the percent change from preoperative baseline in daily step count during the first 2 weeks post-discharge from hospital (measured on Discharge Day, Day +7, and Day +14). percent change from preoperative baseline in daily step count during the first 2 weeks post-discharge from hospital (measured on Discharge Day, Day +7, and Day +14). To recognize that these data may be missing not at random (ie, due to adverse event, distress, or withdrawal of consent), the effect of study intervention on primary endpoint will be modeled jointly with early withdrawal from data collection of that endpoint. Within the joint model, the sub-model for the primary endpoint will use generalized linear mixed modeling (with treatment and covariates as fixed factors, patient ID as random factor), while the other sub-model will analyze time to early withdrawal (Aim 3's primary endpoint) using proportional hazards regression. Similar joint modeling will be carried out for Aim 1's secondary endpoints (change from baseline in sedentary time, general symptoms, disease-specific symptoms).

Aim 2 – Because the CCI is derived from data routinely entered in the medical chart, no loss to follow-up is anticipated for this endpoint. A sample size of 332 subjects randomized 1:1 will provide (per East 6.5 software) 88% power to detect the hypothesized CCI benefit, using a 1-sided test of proportions, unpooled estimate of variance, critical p-value for efficacy=0.024, cumulative alpha=0.025.

The Aim's primary endpoint will be maximum Comprehensive Complications Index (CCI) during the 30 days post-discharge. Maximum CCI will be categorized as above vs below 15, and logistic regression will be used to evaluate the effect of study intervention. The Aim's secondary endpoint, time to hospital readmission through 90 days, will be subjected to survival analysis, handling any early withdrawal from study as a competing endpoint.

Aim 3 - The trial's sample size of n=332 will provide (per SAS software, PROC POWER for two-sample comparison of proportions) at least 80% power.

Treatment will be evaluated for association with this Aim's primary endpoint, time to early withdrawal, using proportional hazards regression. This analysis will be generated as a sub-model of the joint modeling for Aim 1.

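### The primary step endpoint names three measurement days from a daily record; the plan does not say how daily counts become those values or which period the 4-weekday-plus-1-weekend-day minimum covers

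*Combined protocol and SAP*

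**What the plan says.** Section 13.2 (Aim 1), repeated in the synopsis under Statistical Considerations, sets the primary endpoint as percent change from preoperative baseline in daily steps over the two weeks after discharge, "measured on Discharge Day, Day +7, and Day +14". No averaging window is given for any of the three days.

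Section 13.2 (Data Management) says that "functional recovery data will be continuously recorded on a daily basis over the study duration".

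Section 12.1.3 (Functional Activity) has two wear rules:
- A multi-day rule: "A minimum of 4 weekdays and 1 weekend day with at least 600 minutes (10 hours) of daily wear time will be considered valid". It names no window and no time point.
- A single-day rule: "In order to be considered a valid day, patients need to wear the accelerometer for at least 10 waking hours (600 minutes").

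The Study Calendar (section 10.0) labels the first postoperative step assessment "Pre-Discharge (T2"), not Discharge Day.

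The sample size paragraph for Aim 1 claims "80% power to detect the hypothesized 14% difference in slope due to study intervention", "using a 1-sided, repeated measures-difference of slope test with alpha=0.025". It gives no standard deviation, residual variance or within-patient correlation. The model description lists treatment and covariates as fixed and patient as random. It names neither a time term nor a correlation structure.

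**The concern.** An analyst could not build the primary endpoint from this text without inventing a rule. Three things are open: whether the Day +7 value is one day's count or a summary of the days around it; whether the 4+1 minimum applies to the endpoint, to baseline or to both; and whether the first value is taken in hospital, on the day of going home, or across the two.

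Two things are at stake. If these choices are made after data are seen, the primary result depends on decisions that were not prespecified. And if the three-day wording is followed, most of a record that is being collected anyway goes unused, while the slope rests heavily on the least well-defined day.

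**Working it through.** **1. The plan's own power figure.** Treat the comparison as a two-sample test of per-patient slopes. The implied SD, on the same scale as the 14% difference, is SD = 14 / [(1.960 + 0.842) × √(2/n)].
- n = 166 per arm (332/2): SD ≈ 45.5.
- n = 133 per arm (166 × 0.8 = 132.8, after the planned 20% attrition): SD ≈ 40.8.

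The 80% can only be back-solved in this way. It cannot be reproduced, because no variance input is stated. For assumed SDs of 30, 40, 50 and 60, power at 166 per arm is 0.99, 0.89, 0.72 and 0.57.

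**2. Days used.** Day 0 to Day 14 is 15 days. Three named days are 3/15 = 20%, leaving 12 unused.

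**3. The 4+1 minimum.** It needs 5 qualifying days. One day per time point supplies 1, and all three together supply 3, so single-day values cannot meet it if it applies to them. Windows can: over all seven possible starting weekdays, any run of 6 or 7 consecutive days contains at least 4 weekdays and 1 weekend day. A 5-day run does so for 2 of 7 starts. Look-back windows ending on Day 7 and Day 14 could therefore comply. Discharge Day could not be handled in the same way, because a window before it is inpatient and a window after it overlaps the Day 7 window.

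**4. What the slope uses.** With times 0, 7 and 14 the mean is 7 and Sxx = 49 + 0 + 49 = 98. A complete patient's least-squares slope is (−7·y0 + 0·y7 + 7·y14)/98 = (y14 − y0)/14. Day 7 has zero weight, so the slope is the difference between Day 14 and Discharge Day.

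**5. How different the readings of Discharge Day could be.** Pilot medians in section 2.4 are 6,562 steps before surgery, 483 in hospital and 2,483 in the first two weeks after discharge. As ratios of medians, 483/6,562 = 7% and 2,483/6,562 = 38%, about 30 points of baseline apart. This bounds the shift in the first reading only roughly, and it would be common to both arms.

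**6. Precision from using every day.** With independent days, within-patient slope variance is σ²/Sxx. Sxx is 98 for days {0, 7, 14} and 280 for Days 0–14, so the ratio is 98/280 = 0.35. Under AR(1) correlation ρ between adjacent days, generalised least squares gives the following ratios to the three-day variance, which is 2σ²(1 − ρ¹⁴)/196:

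| ρ (assumed) | All days 0–14 | All days 1–14 | Two weekly means |
|---|---|---|---|
| 0 | 0.35 | 0.43 | 0.57 |
| 0.3 | 0.55 | 0.67 | 0.91 |
| 0.5 | 0.72 | 0.87 | 1.23 |
| 0.7 | 0.91 | 1.06 | 1.55 |
| 0.9 | 1.00 | 1.12 | 1.55 |

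Using all days from Discharge Day on is never worse in this range. Dropping Discharge Day, or collapsing to two weekly means, can lose precision because the time span shortens. All ratios concern the within-patient component only. Variation in true slopes between patients is not reduced by more days.

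**The case against.** The strongest reply is that the documents do not contradict themselves. A reader might infer that the endpoint can never satisfy its own validity rule. That is not established. The 600-minute rule can be met on a single day, no text applies the 4+1 minimum to each time point, and 6- to 7-day windows at Day 7 and Day 14 would meet it. The named days may also be schedule labels: the Study Calendar uses the same columns for complications and readmissions, which are not one-day measures. This stands, and it limits the point to an undefined derivation.

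A reader might also infer a fixed, large loss of efficiency, for example from the variance of a 7-day mean against one day. That is the wrong quantity for a slope test, and it needs a correlation that the documents do not give. For the slope, the gain runs from substantial to nil. Estimates of how many patients would fail a weekly wear rule are similarly unsupported: the pilot's 88% is an overall pedometer adherence rate, not a daily probability of 600 minutes' wear.

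Last, hospital and home activity mix on Discharge Day in both randomised arms, so no between-arm bias is shown. That is right. The problem there is definition and noise.

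What survives is that no permitted reading is written down, and that the wording as it stands names three days out of a daily record.

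**Conclusion.** The point holds as a gap in the definition of a primary endpoint, together with an inexpensive chance to use data already being collected. On the stated wording, 3 of 15 days are used, the slope for a complete patient depends on Day 14 minus Discharge Day, and that first day carries two different labels. Modelling all valid days multiplies the within-patient slope variance by 0.35 to about 1.00 over AR(1) correlations from 0 to 0.9. That range is an assumption, and the overall gain is smaller wherever patients' true slopes differ. The documents do not support a claim that the endpoint is impossible to derive, that it is biased between arms, or that the trial is underpowered; the 80% simply cannot be checked. Should-fix, moderate confidence.

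**What to change.** Amend section 13.2 and the matching synopsis text before any unblinded analysis:

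1. Enter every day from Discharge Day to Day 14 with at least 600 minutes of wear as a repeated measure in the planned mixed/joint model. Include time as a continuous term, its interaction with treatment (the slope difference is what is powered), and a serial-correlation structure so that adjacent days are not treated as independent.
2. State that the 4+1 minimum applies to the preoperative baseline only, and give the baseline window.
3. Reconcile Discharge Day in section 13.2 with the pre-discharge label in section 10.0, and add a sensitivity analysis without that day. Keep it in the main analysis, since removing it shortens the span and can cost precision.
4. Restate the Aim 1 power for this definition, giving the slope SD (or residual and between-patient components), the assumed correlation, and the units of the 14% difference.

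The cost is SAP wording, a slightly more complex model and a new power run. No extra data collection is needed. One caution: if recovery is curved, a linear slope through 15 days is not the same quantity as the end-to-end change, so the assumed shape should be stated.

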Monitoring Postoperative Recovery from Cancer Surgery is Challenging after Discharge. Due to changes in healthcare and advances in surgical techniques, surgeons are asked to discharge patients earlier after surgery. Operations that were previously associated with 10-20 day hospital stays are now outpatient or short-stay procedures. Postoperative complications that traditionally arise in the hospital are also developing in the community and at home. The current delivery model for post-discharge care is largely inefficient and not proactive.³² Home health nurses are often dispatched for unresolved acute problems. Patients may contact the hospital when acute problems arise, but are often unaware of when to contact their surgeons (RQ-3). This often requires hours or days to resolve, and is burdensome for patients, families, and the healthcare system. Delays in communicating critical conditions may escalate problems beyond outpatient care. In critical situations, emergency room visits within the same healthcare system or at a different institution occur, resulting in inefficient and fragmented care.

The burden of postoperative hospital readmissions after major cancer surgery is high.³³⁻³⁵ Depending on the tumor site, 90-day readmission rates for major cancer surgery range from 23-43%.³⁶ Published data suggest that 30- and 90-day readmission rates are 30% and 43% for cystectomy, and 22% and 35% for esophagectomy and pancreatectomy.^{36, 37} Hospital readmissions are burdensome, and result in higher 1-year mortality rates, and delays in timing and eligibility for adjuvant therapies.³³ Predictors of readmissions are similar across different tumor sites, and include functional impairments, comorbid conditions, and postoperative complications.^{36, 38}

There are Critical Knowledge Gaps on the Impact of Patient-Centered Outcomes in Cancer Surgery. The impact of routine symptom monitoring is predominantly tested in chemotherapy settings.^{39,40} These findings suggest a positive effect on patient-provider communication⁴¹⁻⁴⁴, detection of unrecognized problems^{40, 44-47}, guiding clinical care^{46, 48-50}, health outcomes⁵⁰⁻⁵⁴, and survival.⁹ Few studies are conducted in surgical oncology, and few

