The third component involves a real-time, alert/feedback system based on pre-determined outcome thresholds. Alerts are triggered in real-time based on patient input into the TapCloud™ application. Pre-determined thresholds include: 1) daily steps of ≤ 1500 ; or 2) one or more symptoms rated 4 or greater (moderate-severe intensity). When thresholds are met, trained clinical RNs will receive secure alerts via the TapCloud™ application. The clinical RNs will initiate contact with patients via secure messaging through the application as a first attempt to assess and remedy the problem. If unsuccessful, telephone calls will be used to further assess, triage, manage, and resolve the issue. **Figure 4** provides a graphic depiction of the telemonitoring care design. All participants will also receive standard surgical care.

[figure not shown]

Figure 4. Perioperative Telemonitoring Care

Surgeon Only Perioperative Care - The “standard perioperative care” includes surgeon/surgical team management of functional declines/symptoms. Patients/families will meet with the surgeon at least once prior to surgery, have pre-anesthesia clinic visit for pre-op final evaluation, be managed daily during postop inpatient acute care, have first postop visit 1-4 weeks after discharge, with follow-up as needed thereafter. Patients may or may not undergo prehabilitation as this is not the current standard of care for the participating sites. Referral for functional and nutritional prehabilitation are at the discretion of the surgeon/surgical team. There are no scheduled contacts with the patient between discharge and 1-4 weeks after. Patients/families are instructed to follow the standard procedures for reporting problems between clinic visits, including: 1) contacting their surgical team if symptoms become severe and physical function worsens; and 2) use of the hospital call line to report problems.

Study Procedures

Following informed consent, a brief, 1-item health literacy screen (Screening Question for Limited Health Literacy) will be completed. Research staff will provide additional support (written instructions, telephone calls) for patients with limited health literacy. The Accrual/Evaluation RNs will engage patients in understanding the type and method of data collected, and how the data will be used to support decisions on personalized perioperative care.

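### Aim 2: the opportunity to detect post-discharge complications differs by arm, and the plan describes no arm-neutral way of finding them

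*Combined protocol and SAP*

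**What the plan says.** All references are to the combined protocol and SAP.

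- **Source of the endpoint.** Section 13.2 (Aim 2): "Because the CCI is derived from data routinely entered in the medical chart, no loss to follow-up is anticipated for this endpoint". The window is the 30 days after discharge, and "Maximum CCI will be categorized as above vs below 15, and logistic regression will be used to evaluate the effect of study intervention".
- **Power.** Section 13.2: "A sample size of 332 subjects randomized 1:1 will provide (per East 6.5 software) 88% power to detect the hypothesized CCI benefit". The calculation there compares two proportions one-sided, without pooling the variance, at a critical p-value of 0.024. No event rate is given for either arm.
- **Readmissions and emergency visits.** Section 12.1.3 takes these from an audit of the electronic health record. For care elsewhere it says: "If the patient seeks emergent care outside of the primary institution, the patient's permission will be obtained to review these records". This is written under Readmissions, not under CCI, and nothing says how staff would learn that outside care took place. Section 2.1 accepts that such care happens: "emergency room visits within the same healthcare system or at a different institution occur".
- **Contact after discharge.** Under Section 5.1, nurses in the telemonitoring arm message and then telephone patients whose steps or symptoms cross a threshold. For surgeon-only care: "There are no scheduled contacts with the patient between discharge and 1-4 weeks after". Until then, patients are expected to report problems themselves.
- **Contact without arm limit.** Section 5.5 has Research Nurses and CRAs review responses to the outcome measures and alert the surgeon to serious conditions. Section 13.2 provides reminders, and staff contact when data are missing.
- **Grading.** Section 4.4 mentions masking only before assignment. No section says who grades the CCI or whether grading is masked.

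**The concern.** A complication that never reaches the chart does not appear as missing data. It adds nothing to the CCI, and the patient may be counted below 15. An expectation of no loss to follow-up therefore does not show that events are captured.

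Incomplete capture matters most when it differs between arms, and here the intervention is itself a route of detection. A threshold crossing prompts a nurse to ask what is wrong. A surgeon-only patient with the same problem may call, may wait for the visit, or may go elsewhere. The CCI depends partly on less severe complications that never lead to admission, and these are the most exposed.

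At stake is whether the Aim 2 contrast reflects how often complications occur or how often they are recorded. If control events are missed, a true benefit shrinks. If problems settled by secure message go uncharted, telemonitoring looks better than it is.

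**Working it through.** **Step 1: could shared procedures close the gap?** The review of responses in Section 5.5 can reveal only what the instruments ask. Those listed in Section 12.1.3 for repeated use are the MDASI (13 symptoms, 6 interference items) and one item comparing today with yesterday. Neither asks about complications, treatment for them, or care elsewhere. The staff contacts in Section 13.2 concern reminders, device wear and missing data. So the shared procedures help, but they do not query the endpoint.

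**Step 2: the plan's 88%.** It cannot be reproduced, because no rates are stated. Inputs that are stated: 332 randomized 1:1, so n = 166 per arm; one-sided; unpooled variance; critical p-value 0.024, so z = 1.977. With control rate pC and telemonitoring rate pT,

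power = Φ( (pC − pT) / √[(pC(1−pC) + pT(1−pT)) / n] − 1.977 ).

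Solving for 88% at assumed control rates gives these pairs: 20% vs 8.1%, 30% vs 15.7%, 40% vs 24.1%, 50% vs 33.2%. Check at 30% vs 15.69%: the standard error is √[(0.2100 + 0.1323)/166] = 0.0454; 0.1431/0.0454 = 3.151; 3.151 − 1.977 = 1.174; Φ = 0.88. Using alpha 0.025 instead gives 88.3%, and pooled variance at 0.024 gives 87.4%, so the variant hardly matters. The formula ignores covariate adjustment in the logistic model.

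**Step 3: control arm under-captured, true benefit present.** Replace pC by pC × (1 − m), where m is the assumed share of control patients above the cut who are missed. Telemonitoring capture is set at 100%. Example with pC = 30% and m = 10%: the observed control rate is 27%; the standard error is √[(0.1971 + 0.1323)/166] = 0.0445; 0.1131/0.0445 − 1.977 = 0.56; Φ = 0.71.

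| True rates | m = 0 | m = 5% | m = 10% | m = 20% |
|---|---|---|---|---|
| 20% vs 8.1% | 88% | 83% | 76% | 59% |
| 30% vs 15.7% | 88% | 81% | 71% | 47% |
| 40% vs 24.1% | 88% | 79% | 66% | 36% |
| 50% vs 33.2% | 88% | 76% | 60% | 25% |

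**Step 4: no true effect, 10% miss in one arm.** At a true rate of 30%, the observed rates are 30% and 27%: the standard error is √[(0.2100 + 0.1971)/166] = 0.0495; 0.03/0.0495 − 1.977 = −1.37; Φ = 8.5%. At 40%, the observed rates are 40% and 36%: the standard error is √[(0.2400 + 0.2304)/166] = 0.0532; 0.04/0.0532 − 1.977 = −1.23; Φ = 11%. Without a differential miss the figure is 2.4%.

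- If the control arm is under-captured, 8.5-11% is the chance of apparent harm at the same critical value, and the chance of false benefit falls to 0.3-0.5%.
- If the telemonitoring arm is under-captured, 8.5-11% is the chance of false benefit.

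**The case against.** The case on the other side is substantial.

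- **The planned source is the same in both arms.** The chart is used for everyone, and Section 10 schedules CCI at the same time points for all. Unequal capture is a risk, not something the plan states.
- **Nurse contacts may never feed the CCI.** A reader might infer that they reveal events which then enter the chart. No section says so. The described flow runs from TapCloud to a dashboard and a research database. The inference should not be stated as fact.
- **Control patients are not without staff contact.** A reader might infer that only telemonitoring patients have nurse contact. Sections 5.5 and 13.2 do not support that; only alert-driven triage is specific to one arm.
- **The control visit falls inside the window.** One to four weeks is 7 to 28 days, and the endpoint covers 30, so earlier events can be charted then. This reduces the gap but depends on what is asked and recalled at the visit.
- **Silence is not a statement.** The plan does not say that the CCI grader knows the allocation; it does not identify the grader at all. Consent pages are not in the reviewed text, and Section 12.1.2 mentions a HIPAA authorization, so permission for outside records may already be taken.
- **The miss rates have no source in the documents.**

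These points limit the claim to a difference in opportunity, of unknown size and direction. They do not remove it, because nothing described asks both arms the same question about the endpoint.

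**Conclusion.** The point holds as a difference in detection opportunity without a described safeguard. The expectation of no loss to follow-up does not cover events that stay out of the chart.

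A reader might go further and conclude that the bias runs against telemonitoring. The documents do not support a direction: control events may be missed, or problems resolved by message may go unrecorded. Nor does the point carry over equally to 90-day readmission. Home-institution readmissions are found by record audit in either arm and are little affected; admissions elsewhere are exposed.

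The size is illustrative only. It rests on assumed control rates of 20-50%, assumed relative misses of 5-20%, full capture in the other arm, and an unadjusted comparison of 166 per arm at one-sided 0.024. Within those assumptions even a 5% miss costs 5 to 12 points of power, so a modest asymmetry would matter. The remedy is cheap, and events not recorded at the time are hard to recover later. The plan should therefore be changed.

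**What to change.** 1. Add one identical short question set to the existing Day 7, 14, 30, 60 and 90 assessments in both arms: any emergency visit, admission or new treatment for a complication, at any institution, since the last assessment.
2. Extend the outside-records provision in Section 12.1.3 from readmissions to CCI, with the patient's permission.
3. Revise the loss-to-follow-up sentence in Section 13.2 to say how uncharted and outside events will be found.
4. Say who grades the CCI. Where existing staff allow, use study clinicians who do not triage alerts, without sight of alert notes.
5. Record how each event was first detected, for description only. Do not exclude events known only through nurse contact: that removes real events from one arm. With equal 30% rates, dropping 10% of telemonitoring events gives 27% vs 30%, the same 8.5% false-benefit chance as in the calculation.

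The plan should also state the assumed CCI rates, so that the 88% can be checked.

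Cost: a protocol amendment, a few questions at scheduled assessments, one extra data field, slight patient burden and some record retrieval. No new visits are needed. Withholding alert notes from graders takes preparation, so that step depends on staff capacity.
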